## 1. Synopsis

Type of application	Clinical Trial
Sponsor	Medica Scientia Innovation Research (MedSIR) [name] Tel.: [name]; Fax: [name]
Clinical trial title	“A phase II clinical trial of radium-223 activity in patients with metastatic castration-resistant prostate cancer (mCRPC) with asymptomatic progression while on abiraterone acetate or enzalutamide besides AR-V7 mutational status”
Protocol number	MedOPP098
Study Coordinator and Principal Investigator	[name] [name] Hospital Vall d’Hebrón
Expected sites	10 sites are expected to participate in Spain.
Central Ethics Committee/Institutional Review Board	Corporació Sanitaria Parc Taulí
Name and qualification of the persons in charge of Monitoring	[name] Medica Scientia Innovation Research (MedSIR) [name] [contact]; [contact]
Investigational drug	Radio 223 (Xofigo®)
Trial phase	II
Objectives	
Primary objective
 
To assess the efficacy of radium-223 in asymptomatic patients with mCRPC who have progressed while on abiraterone acetate or enzalutamide treatment.
 
Secondary objectives
 

• Safety profile.

• To determine the association between AR-V7 status (positive vs. negative) and progression-free survival (PFS).

• To establish the relationship between circulating tumor cells (CTCs) number with radium-223 efficacy.

Design	Multicenter, single-arm, open-label, non-controlled phase IIa clinical trial.

Primary endpoint	The primary endpoint of this study is to assess the efficacy of radium-223 in terms of radiological rPFS.
Study population and total number of subjects	Patients ≥ 18 years of age diagnosed with mCRPC with bone metastases and asymptomatic progression after at least 24 weeks of treatment with abiraterone acetate or enzalutamide. A total of 52 patients will be enrolled into this trial. We expect to include 13 AR-V7-positive and 39 AR-V7-negative patients
Approximate duration of subject participation	Patients will be treated with radium-223 at four-week intervals for six intravenous injections.  Patients who complete the study treatment during its active treatment phase will enter a follow-up period with radiological tumor assessment every three months (±7 days) from the last dose of study treatment until documented disease progression.
Calendar and estimated completion dates	Start Recruitment (FPI): Nov-2016 End of Recruitment (LPI): Oct-2018 Follow-up period for progression: Sep-2019 Follow-up extension for safety: Apr-2021 Final report: Mar-2018 Final safety report: Aug-2021

### 3. Abbreviations

AE:	Adverse events.
AF:	Alkaline Phosphatase.
AR-V7:	Androgen Receptor Splice Variant-7.
CI:	Confidence Interval.
CTC:	Circulating Tumor Cells.
IC:	Informed Consent.
mCRPC:	metastatic Castration-Resistant Prostate Cancer.
MedDRA:	Medical Dictionary for Regulatory Activities.
OS:	Overall Survival.
PCWG:	Prostate Cancer Clinical Trials Working Group.
PFS:	Progression-Free Survival.
PT:	Preferred Term.
rPFS:	radiological Progression-Free Survival.
SAE:	Serious Adverse Events.
SOC:	System Organ Class.
SSE:	Symptomatic Skeletal Event.

## 4. Introduction

### 4.1 General

The present study (EXCAAPE) is a phase II clinical trial of radium-223 activity in patients with metastatic castration-resistant prostate cancer (mCRPC) with asymptomatic progression while on abiraterone acetate or enzalutamide besides AR-V7 mutational status.

The purpose of this statistical analysis plan (SAP) is to provide a protocol specific description of the statistical analysis that will be performed to produce an integrated clinical/statistical report.

This SAP is based upon the following study documents:

- Initial protocol version dated: 29th July 2016
- Protocol version dated: 20th December 2016
- electronic Case Report Form (eCRF), Version 4.0

### 4.2 Type of study

This a phase II clinical trial of radium-223 activity in patients with metastatic castration-resistant prostate cancer (mCRPC) with asymptomatic progression while on abiraterone acetate or enzalutamide besides AR-V7 mutational status.

### 4.3 Study Protocol Amendments

- Initial protocol version dated: 29th July 2016
- Protocol version dated: 20th December 2016

### 4.4 Study Population

Patients with mCRPC with asymptomatic progression while on abiraterone acetate or enzalutamide. The progression on enzalutamide or abiraterone acetate will be defined as patients who confirm radiographic progression and/or PSA progression with rapid PSA doubling time (less than three months).

### 4.5 Study Design

A total of 52 patients will be enrolled into this trial. We expect to include 13 AR-V7-positive and 39 AR-V7-negative patients.

The design of this study is divided into three well-defined phases:

- **Screening phase**

Subject eligibility is determined, including the documentation of baseline characteristics. This phase of the study will begin once the informed consent is signed by the patient.

- **Treatment phase:** Once the informed consent has been signed and the study screening criteria have been confirmed, the patient will be treated with radium- 223 at a dose of 55 kBq (after 2015 NIST implementation) per kilogram body weight, given at four-week intervals for six intravenous injections.

Patients will receive study treatment according to the protocol and will be prematurely discontinued in the following situations: disease progression, occurrence of unacceptable side effects, death, or withdrawal of consent, whichever occurs first.

- **Follow-up phase:**

Once the treatment phase is completed, patients will enter a follow-up period with radiological tumor assessment every three months ( $\pm 7$  working days) until disease progression and safety evaluation during 2 years from the last dose of study treatment. If patient discontinued treatment for any reason other than progression, tumor reevaluation will be included in the assessment. After disease progression, a safety follow-up visit will be performed within three following months and 2 years after last dose of study treatment (including survival status and post-study anticancer therapy evaluation). Safety evaluation after progression will include follow-up of symptomatic skeletal related events and overall survival.

#### **4.6 Study Schedule**

The schedule of visits for this study and procedures to be performed at each visit are shown in the appendix 1 of the protocol.

#### **4.7 Sample Size**

A total of 52 patients will be enrolled into this trial. We expect to include 13 AR-V7-positive and 39 AR-V7-negative patients.

##### Justification of sample size

The sample size is determined on the basis of the primary endpoint. The primary endpoint is defined as PFS according to the PCWG2 criteria. We will screen the AR-V7 mutation retrospectively, after the patient was included. We expect the number of AR-V7-positive patients will be 25% of total sample. Therefore, sample size has been estimated on AR-V7-positive cohort to ensure a minimum of 80% power in two cohort analysis. We hypothesized equally efficacy of radium-223 in AR-V7-negative and AR-V7-positive cohorts.

Previous studies in advanced refractory prostate cancer patients treated with docetaxel plus estramustine against mitoxantrone plus prednisone showed a median PFS of 6.3 and 3.2 months, respectively. According to these results, excluding a PFS  $\leq 3$  months while targeting an improvement of the PFS  $\geq 6.3$  months would be a conservative approach to evaluation of the radium-223 effect in both cohorts. The analysis will be performed with one arm one-sided Log-Rank test.

A maximum follow-up period of 34 months is planned. We assume an uniform accrual of 2.26 patients per month (both cohorts). A sample size of 52 patients will be needed to attain 80%

EudraCT number: 2016-001888-36

power at nominal level of one-sided alpha of 0.05. Therefore, we expect to include a total sample of 52 patients, 39 of them will be AR-V7-negative and 13 AR-V7-positive patients. Safety follow-up extension of the study.

The maximum follow-up of the study for primary and secondary efficacy analysis will be 34 months. However, we will include a 2-years extension after the end of the treatment (April 2019) to evaluate bone lesions. Additionally, analysis of overall survival will be also extended.

## 5. Study objectives and variables

### 5.1 Primary objective(s) and primary endpoint(s)

#### **Primary objective:**

To assess the efficacy of radium-223 in asymptomatic patients with mCRPC who have progressed while on abiraterone acetate or enzalutamide treatment.

#### **Primary endpoint:**

To determine the efficacy of radium-223 in terms of radiological PFS (rPFS).

### 5.2 Secondary objective(s) and secondary endpoints

#### **Secondary objectives:**

- Safety profile.
- To determine the association between AR-V7 status (positive vs. negative) and rPFS.
- To establish the relationship between CTCs number with radium-223 efficacy.

#### **Secondary endpoints:**

##### Safety:

AEs will be evaluated using the Common Terminology Criteria for Adverse Events (CTCAE) of the US National Cancer Institute (NCI) version 4.0. AEs and serious adverse events (SAEs) will be assessed to determine the safety and tolerability of the various combinations of drugs.

##### Efficacy:

- Radiographic progression-free survival (rPFS) depending on AR-V7 status.
- Overall survival (OS).
- Time to first symptomatic skeletal event (SSE).
- Time to PSA progression according to the ALSYMPCA study criteria.
- Determination percentage of PSA progression.
- Alkaline phosphatase level response (AF), normalization of alkaline phosphatase level, according to the ALSYMPCA study criteria.

##### Molecular aspects:

- Assessment of AR-V7 mutation evolution during the study treatment.
- Determination changes in CTCs number during the study treatment.

### **5.3 Safety evaluation**

The safety evaluation has been included in secondary objective (see 5.2).

## **6. Analysis sets**

### Full analysis set

All patients that accomplish selection criteria and receive at least one dose of study medication.

### Per protocol set (PP)

All patients that accomplished selection criteria, received the study drug according to protocol timelines and dosing, and had no major protocol deviations. Criteria for determining the PP group assignment would be established by the Steering Committee before the statistical analysis begins. Patients without AR-V7 status in the study will be excluded.

### Modified full analysis set

All patients with determination of CTC that accomplish selection criteria and receive at least one drug dose.

### Safety set

The safety set includes patients who receive at least one dose of study medication.

The primary analysis of efficacy will be performed in the full analysis and per protocol sets in all patients. Secondary and subgroup analysis of efficacy will be also performed in the full analysis and per protocol sets all patients and two study cohorts (AR-V7-negative and positive). Analysis of CTC will be performed in modified full analysis set in both cohorts and all study patients. Safety analyses will be performed in the safety set in both cohorts and all study patients.

### **6.1 Protocol Deviations**

Protocol deviations will be recorded in the EXPERIOR database. A by-patient listing of protocol deviations and a by-patient listing of inclusion and exclusion criteria not met will be provided.

Major protocol deviations are defined as those deviations from the protocol likely to have an impact on the perceived efficacy and/or safety of study treatment.

To determine the per protocol set, all protocol deviations will be reviewed prior to database lock to determine which ones should be classified as major deviations. Patients with major protocol deviations will be excluded from the per protocol set.

Major protocol deviations may be discussed in the data review meeting. Criteria for determining full analysis set would be established by the Steering Committee (SC) before the statistical analysis begins.

Major protocol deviations and any action to be taken regarding the exclusion of subjects or affected data from specific analyses are defined below.

A summary of the number and percentage of subjects with a major protocol deviation by type of deviation will be provided. Also, a by-subject listing of major and minor protocol deviations will be provided.

Description	Category	Grade*	Rationale	Comments
Adult < 18 years	Inclusion/Exclusion criteria	Major	Safety	Automatic check
Informed consent form not signed	Inclusion/Exclusion criteria	Major	GCP breach	Automatic check. Patient data could not be used for efficacy assessment
Patient has not histologically confirmed adenocarcinoma of the prostate without neuroendocrine differentiation or small cell features	Inclusion/Exclusion criteria	Major	Efficacy	Manual Review
Patient has not bone metastases due to the prostate cancer and presence of visceral metastases	Inclusion/Exclusion criteria	Major	Efficacy	Manual Review
Serum testosterone of > 1.7 nmol/L (or > 50 ng/dL) at screening	Inclusion/Exclusion criteria	Major	Efficacy Safety	Automatic check
<24 weeks of treatment with abiraterone acetate or enzalutamide within its approved label indication and discontinuation <4 weeks prior to start of study drug at day 1	Inclusion/Exclusion criteria	Major	Efficacy Safety	Manual Review

EudraCT number: 2016-001888-36

Castration-naïve patients treated >six cycles with docetaxel	Inclusion/Exclusion criteria	Major	Efficacy	Manual Review
Patient does not receive and will not continue to receive ongoing androgen deprivation with luteinizing releasing hormone (LHRH) analogue therapy throughout the course of the study or has not had a bilateral orchectomy	Inclusion/Exclusion criteria	Major	Efficacy	Manual Review
Patient is not asymptomatic from prostate cancer (score on brief pain inventory short form (BPI-SF) Question #3 is not zero or one and use of opiate analgesics for prostate cancer-related pain currently or anytime within two weeks prior to screening)	Inclusion/Exclusion criteria	Major	Efficacy	Automatic check and Manual Review
ECOG >1 at screening	Inclusion/Exclusion criteria	Major	Safety	Automatic check
Patient receiving bisphosphonate or other approved bone-targeting therapy on non stable doses for at least four weeks prior to start of study drug at day 1	Inclusion/Exclusion criteria	On case by case	Efficacy	Manual Review
Life expectancy $\geq$ 12 months	Inclusion/Exclusion criteria	On case by case	Efficacy	Manual review on medical history

Participation in another interventional study while on study drug	Inclusion/Exclusion criteria	Major	Efficacy Safety	Manual review on medical history
Not use of two acceptable methods of birth control from screening until six months after final study drug administration	Inclusion/Exclusion criteria	Major	Efficacy Safety	Manual review on medical history
Patient has received any anti-neoplastic therapy following abiraterone acetate or enzalutamide discontinuation and prior to start of study drug at day 1	Inclusion/Exclusion criteria	Major	Efficacy	Manual Review
Patient has known or suspected brain metastases or active leptomeningeal disease	Inclusion/Exclusion criteria	Major	Efficacy Safety	Manual review
Subject has concurrent disease or any clinically significant abnormality at screening, which would interfere with the subject's participation or evaluation of study results.	Inclusion/Exclusion criteria	Case by case	Efficacy Safety	Manual review. If it is likely to interfere with study procedures or with response to study treatment**
Subject has a history of another invasive cancer within three years prior to Screening	Inclusion/Exclusion criteria	Case by case	Efficacy Safety	Manual review on medical history
Subject had major surgery within one month prior to	Inclusion/Exclusion criteria	Case by case	Safety	Manual review

EudraCT number: 2016-001888-36

screening				
Subject has received investigational therapy within 28 days or 5 half lives, whichever is longer, prior to start of study drug at day 1.	Inclusion/Exclusion criteria	Major	Efficacy Safety	Manual review
Absolute neutrophil count < 1,500/ $\mu$ L, at screening	Inclusion/Exclusion criteria	Case by case	Efficacy Safety	Automatic check
Platelet count < 100,000/ $\mu$ L, and hemoglobin < 6.25 mmol/L (or < 10 g/dL) at screening	Inclusion/Exclusion criteria	Major	Efficacy Safety	If clinically relevant** Automatic check
Subject has received growth factors or blood transfusions within seven days of the hematologic laboratory values obtained at screening	Inclusion/Exclusion criteria	Major	Efficacy Safety	Manual review
Subject has total bilirubin > 1.5 times the upper limit of normal (ULN) at screening, except for subjects with documented Gilbert's syndrome.	Inclusion/Exclusion criteria	Case by case	Efficacy Safety	Automatic check and Manual review
Subject has creatinine > 2.5 mg/dL at screening.	Inclusion/Exclusion criteria	Case by case	Efficacy Safety	Automatic check
Subject has albumin $\leq$ 30 g/L (or $\leq$ 3.0 g/dL) at screening.	Inclusion/Exclusion criteria	Case by case	Efficacy Safety	Automatic check
IMP not administered but screening completed	Inclusion	Major	Efficacy	Study discontinuation prior to treatment start

EudraCT number: 2016-001888-36

Hypersensitivity to IMP	Investigational Medicinal Product	Major	Efficacy Safety	Major if dose not administered completely
IMP overdose	Investigational Medicinal Product	Major	Efficacy Safety	
IMP underdose	Investigational Medicinal Product	Major	Efficacy Safety	
IMP administration dosing/Schedule/delays	Investigational Medicinal Product	On case by case	Efficacy Safety	If administered dose is systematically deviating from expected dose and delays not as described in protocol
IMP toxicity	Investigational Medicinal Product	On a case by case	Safety	If toxicity has not managed appropriately Listing with AE's grade 3/4 with action = none before the EOT date
Post-baseline tumor assessment not done	Study procedure	Major	Efficacy Safety	Major if no post baseline assessment done or if first post-baseline assessment is not at least after 8 weeks of treatment start.
Post-baseline tumor assessments out of the window	Study procedure	Minor	Efficacy	If done more than every 12 weeks +7 days. Major if only post-baseline assessment is not at least after 8 weeks of treatment start.
No baseline tumor assessment	Inclusion and Exclusion criteria/ Study procedure	Major	Efficacy	If not baseline values any post-baseline data indicating presence of new bone lesions/visceral lesions could be evaluated as evidence of PD Flag if baseline data (CT and bone scans) are >28 days before day 1 cycle 1.

No post-baseline data indicating presence of ≥ 2 new bone lesions or progression as per RECIST 1.1	Study procedure	Major	Efficacy	No evidence of Radiological PD for patients not discontinued due to increased PSA, symptoms or clinical deterioration.
Visits out of window	Study procedure	Minor	Safety	If not performed every 28 days +7 days until EOT; if not performed every 3 months after EOT or if EOS not performed within 3 months after progression, lost to FUP.
Local laboratory tests out of window	Study procedure	Major	Safety	If tests scheduled for day 1 of all cycles (including screening) not performed within 72 hours prior to the dose
Screening assessments out of window	Study procedure	Case by case	Safety	If done >28 days before day 1 cycle 1. Not applicable to local lab tests.
Assessments not done during treatment period (lab value, HRQoL..)	Study procedure	Case by case	Safety	Not applicable to Radiological Assessments. Flag if systematically not done.
Blood sample for translational study not obtained or obtained at incorrect timepoint	Study procedure	Case by case	Efficacy	Depending on which sample is not collected.
Blood sample for translational study obtained out of window at screening	Study procedure	Case by case	Efficacy	Sample not obtained within 72 hours prior to the first dose
Adequate follow-up	Study procedure	Major	Efficacy	If no post-treatment evaluation according to protocol
Prohibited medication was taken	Concomitant medication	Major	Efficacy	If any therapies intended for the treatment of cancer prior to EoT (Cytotoxic chemotherapy, other systemic radioisotopes,

EudraCT number: 2016-001888-36

				radiotherapy, abiraterone acetate, enzalutamide or any antiandrogen)
Prohibited medication was taken	Concomitant medication	On a case by case	Efficacy Safety	If another investigational drug prior to EoT
Subject not withdrawn as per protocol	Administrative and Other	Major	GCP	If data is obtained after withdrawal

\* Major protocol deviation excludes from the full analysis set

\*\* Identification of clinically relevant conditions from the Medical History

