4.2. Inclusion criteria

Patient eligibility will be reviewed and documented by a suitable member of the investigator's study team before the patients are enrolled in the study.

Patients must meet all the following inclusion criteria to be enrolled in the study:

- Subject is an adult \geq 18 years at the time of informed consent and has signed informed consent before any trial related activities and according to local guidelines.
- Subject has histologically confirmed adenocarcinoma of the prostate without neuroendocrine differentiation or small cell features.
- Subject has bone metastases due to the prostate cancer and absence of visceral metastases.
- Subject has a serum testosterone of \leq 1.7 nmol/L (or \leq 50 ng/dL) at screening.
- Subject must have received a minimum of 24 weeks of treatment with abiraterone acetate or enzalutamide within its approved label indication and has discontinued use at least four weeks prior to start of study drug at day 1.
- Prior use of docetaxel is allowed in castration-naïve patients (maximum of six cycles).
- Subject receives and will continue to receive ongoing androgen deprivation with LHRH analogue therapy throughout the course of the study or has had a bilateral orchiectomy.
- Subject is asymptomatic from prostate cancer, defined as patients with the score on brief pain inventory (short form) (BPI-SF) Question #3 must zero and no use of opiate analgesics for prostate cancer-related pain currently or anytime within two weeks prior to screening.
- Subject has an Eastern Cooperative Oncology Group (ECOG) performance status of 0–1 at screening.
- Subject receiving bisphosphonate or other approved bone-targeting therapy must have been on stable doses for at least four weeks prior to start of study drug at day 1.
- Subject has a life expectancy of more than or equal to 12 months.
- Subject agrees not to participate in another interventional study while on study drug.
- Subject and his female partner who is of childbearing potential must use two acceptable methods of birth control (one of which must include a condom as a barrier method of contraception) starting at screening and continuing throughout the study period and for six months after final study drug administration.

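### Four Major-graded rows of the SAP 6.1 deviation table reverse both halves of an inclusion criterion but keep its joining word, so the castration row flags compliant patients and the other three miss single breaches

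*SAP*

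**What the plan says.** Protocol 4.2 joins the two routes to castration by 'or': "LHRH analogue therapy throughout the course of the study or has had a bilateral orchiectomy". It joins the halves of three other criteria by 'and'. The first is "Subject has bone metastases due to the prostate cancer and absence of visceral metastases". The second is at least 24 weeks of abiraterone or enzalutamide together with at least four weeks off before day 1. The third is a pain-score limit together with no opiates for cancer pain within the stated window.

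The table in SAP 6.1 states the corresponding deviations as follows, all graded Major:

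- Castration: the patient does not receive LHRH "analogue therapy throughout the course of the study or has not had a bilateral orchectomy".
- Metastases: "Patient has not bone metastases due to the prostate cancer and presence of visceral metastases".
- Prior treatment and washout: "<24 weeks of treatment with abiraterone acetate or enzalutamide within its approved label indication and discontinuation <4 weeks prior to start of study drug".
- Asymptomatic status: the row opens by saying that the patient is not asymptomatic, then explains this in a parenthesis: "Question #3 is not zero or one and use of opiate analgesics for prostate cancer-related pain".

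A fifth row, graded case by case, gives the deviation as "Life expectancy $\geq$ 12 months". In protocol 4.2 that is the eligible state.

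The text of SAP 6.1 excludes Major deviators from the per protocol set. The footnote to the table says that a Major deviation excludes from the full analysis set. SAP 6 defines both sets as requiring that the selection criteria were met; the per protocol set also requires no major deviations. SAP 7.1.1 makes the full analysis set primary and the per protocol set supportive. SAP 7.2 and 7.2.2 use both sets for secondary and subgroup analyses.

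**The concern.** The opposite of 'A or B' is 'neither A nor B'. The opposite of 'A and B' is 'A fails or B fails'. The joining word has to change when the halves are reversed, and in these rows it did not.

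The table is more than a label, because SAP 6.1 says that the action to be taken on exclusions is defined there. A false flag at grade Major can therefore remove a compliant patient from an analysis set. A missed flag leaves a real breach out of the planned counts of major deviations by type and out of the major-deviation listing. The trial is open-label and single-arm, so if the wording has to be reinterpreted row by row at data review, that happens with outcomes visible.

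**Working it through.** No figure in the plan has to be reproduced; this is a check of logic.

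**Setting up.** For each criterion let A and B be its two halves, true when the patient satisfies them.

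- Castration: A = ongoing LHRH analogue, B = bilateral orchiectomy. Eligible if A or B. Row as written: not A, or not B.
- Metastases: A = bone metastases, B = no visceral metastases.
- Prior treatment and washout: A = at least 24 weeks, B = at least four weeks off.
- Asymptomatic status: A = pain score within the limit, B = no opiates.
- In the last three, eligible if A and B. Row (or parenthesis) as written: not A, and not B.

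**All four states.**

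| Halves met | Castration: eligible | Castration row flags | Other three: eligible | Other three rows flag |
|---|---|---|---|---|
| A and B | yes | no | yes | no |
| A only | yes | yes (false flag) | no | no (miss) |
| B only | yes | yes (false flag) | no | no (miss) |
| neither | no | yes | no | yes |

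**Counts.** The castration row has 2 false flags. The other three have 2 misses each, 3 × 2 = 6. In total 2 + 6 = 8 of 4 × 4 = 16 states are wrong. With the correct negations, 0 of 16 are wrong. If the opening clause of the asymptomatic row is taken to override its parenthesis, its 2 misses go and 6 of 16 remain.

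**In patient terms.** The castration row flags a patient on an LHRH analogue without orchiectomy, and one with orchiectomy and no analogue. The other three do not flag a patient with both bone and visceral metastases, one with at least 24 weeks of treatment but a short washout, or one on opiates with a qualifying pain score. Their mirror images are missed too: neither bone nor visceral metastases; under 24 weeks with adequate washout; a score above the limit without opiates. A patient who fails both halves is caught. No other row is directed at the missed cases: the anti-neoplastic row covers therapy given after abiraterone or enzalutamide was stopped, and the prohibited-medication row covers concomitant cancer therapy up to the end of treatment.

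**Effect on the analysis sets.** The two kinds of error act differently. A false flag removes a patient who meets the selection criteria, because the per protocol set also demands no major deviation and the footnote extends this to the full analysis set. A missed flag does not admit anyone, because the definitions of both sets already exclude a patient who fails a selection criterion.

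**Size of the castration error.** If all 52 patients meet the criterion and k of them have both an LHRH analogue and an orchiectomy, the row flags 52 − k. The documents do not give k. The range runs from 52 (k = 0) to 0 (k = 52), and is close to 52 only if k is small. SAP 7.4.1 lists the two as separate baseline characteristics, so k will be known.

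**The case against.** The best defence is that nobody would apply the table mechanically. SAP 6.1 has all deviations reviewed before database lock to decide which are major. SAP 6 leaves the per protocol criteria to the Steering Committee before analysis. The castration, metastasis and washout rows are marked for manual review only, and anyone checking against protocol 4.2 would hardly exclude a patient for having just an LHRH analogue. The castration row can pass as clumsy English for 'neither'. The asymptomatic row opens with a correct statement. The life-expectancy row may be a label naming the requirement, as the table's adequate follow-up row does.

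Much of this stands as mitigation. The opening of the asymptomatic row is sound and only its parenthesis is wrong. The life-expectancy row is case by case and excludes nobody automatically. The written rule is still not corrected, and no single charitable reading repairs the table. Reading 'and' as 'either of these' mends the metastasis, washout and opiate wording, but the castration row already says 'or' and still flags compliant patients. Requiring both halves to fail mends the castration row and leaves the misses in the other three.

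A reader might infer that the table keeps patients with visceral disease, short washout or opiate use in the efficacy analyses. The documents do not support that: the set definitions in SAP 6 exclude them independently, and SAP 6.1 also plans a by-patient listing of unmet criteria. The harm from the misses is an incorrect major-deviation summary that disagrees with those definitions. A reader might also infer that essentially all 52 patients would be excluded. That rests on an unstated assumption about k and on literal application without review.

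**Conclusion.** The concern holds as a wrong written rule. Four Major-graded rows are not the negation of the criteria they represent, and 8 of 16 patient states are misclassified (6 of 16 if the opening clause of the asymptomatic row governs). The castration row is the serious one: followed literally, it makes every compliant patient with only one form of castration a Major deviator, excluded from the per protocol set and, by the footnote, from the primary analysis set. The number is 52 − k with k unknown. The other three affect the deviation counts and listing, not who is analysed. The life-expectancy row needs rewording for consistency only. Manual review before lock may soften the practical effect.

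Two neighbouring matters are separate. The pain-score limit differs between the protocol synopsis (zero or one) and protocol 4.2 (zero), and those places must be reconciled. The platelet and haemoglobin row follows the joining word of the protocol's own exclusion criterion and is not an error of negation.

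**What to change.** Before database lock, restate the rows in SAP 6.1 as the true negation of protocol 4.2, one condition per row, keeping the grades already assigned:

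- neither ongoing LHRH analogue nor bilateral orchiectomy;
- no bone metastases;
- visceral metastases present;
- less than 24 weeks of abiraterone or enzalutamide;
- abiraterone or enzalutamide stopped less than 4 weeks before day 1;
- pain-score criterion not met (wording that does not choose between the two limits);
- opiate use within the criterion's window;
- life expectancy under 12 months.

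The cost is a few lines of SAP text. Of the rows concerned, only the asymptomatic one carries an automatic check, so little programming changes. No new data are needed and no eligibility rule is altered.
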